## **12.8 Key Secondary Endpoint**

### **12.8.1 Change from Baseline in HbA1c at 26 Weeks**

The key secondary analysis will be to evaluate equivalence (FDA)/noninferiority (EMA) of Gan & Lee Insulin Glargine Injection relative to Lantus® for HbA1c by comparing the 90% CI with (-0.4%, 0.4%) for equivalence using the TOST approach and by comparing the upper limit of the 95% CI with 0.4% for noninferiority from a pattern mixture model that uses multiple imputation analyzed using Analysis of Covariance (ANCOVA) with treatment included as a fixed effect and baseline HbA1c included as a covariate. Separately in each treatment group, the imputation will use the outcomes of patients who completed the study (including the subjects who discontinued treatment, but provided a visit Week 26 HbA1c sample) to impute outcomes in patients without actual visit Week 26 recorded results under the missing at random assumption. Full details of the multiple imputation procedure will be specified in the SAP. Analysis of HbA1c will follow a hierarchical testing strategy: first, equivalence/noninferiority will be tested with a margin of 0.4%; secondly, if and only if the test using a margin of 0.4% is significant, then equivalence/noninferiority will be tested using a margin of 0.3%. Analyses of HbA1c in the testing hierarchy will be conducted on the Full Analysis Set consisting of all randomized subjects according to randomized treatment with supportive analyses on the Per Protocol Analysis Set. A tipping point analysis with varying assumptions about the differences on each treatment arm between outcomes in patients who withdrew from the study early and outcomes in patients who completed the study will be performed. The estimand of interest for the HbA1c analysis is the difference in change from baseline for HbA1c using the “treatment policy strategy.”

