3.1 Changes from Protocol

Per FDA comment, Wald method has been replaced with logistic regression approach to calculate the difference in proportions along with the corresponding 90% CI for the primary endpoint and corresponding sensitivity analyses. The delta method will be used to calculate the standard error for the difference and the associated confidence interval.

Also, per FDA suggestion, separately in each treatment group, the imputation will use outcomes in patients who discontinued treatment but provided a visit Week 26 glycosylated hemoglobin (HbA1c) measurement if sufficient data are available to impute outcomes in patients without actual visit Week 26 recorded results, under the assumption of missing not at random (MNAR). Full details are provided in Section 11.7 below.

4. Study Objectives

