7.1 General

1) Actual Treatment

The actual treatment received is defined as the IP treatment the subject received during the study, regardless of the treatment the subject was allocated to by randomization. If a subject receives both Gan & Lee Insulin Glargine Injection and Lantus® during the study period for whatever reason, then the actual treatment will be based on the treatment taken on the majority of days during the study.

2) Assessment after EOT

Assessment after EOT is defined as AIA/HbA1c assessment documented after date of EOT visit. If date of EOT visit is missing it is defined as assessment documented after date of last dose of IP + 1 day (to consider assessments of subjects who perform the visit assessment before daily dose of IP).

3) Average Daily Dose of IP

Average Daily Dose is defined as captured on the Average Daily Dose of Study Drug CRF page.

4) Baseline

For each endpoint of interest, unless otherwise noted, the study baseline is defined as the last non-missing assessment taken prior to or on the date of the first dose of study IP. For subjects whose treatment assignment is randomly assigned but not dosed after the randomization visit, the baseline is defined as the last non-missing assessment prior to or on the date of randomization.

5) Change from Baseline

Change from baseline is defined as (value at post-baseline visit – value at baseline).

6) Completer Week 26

A subject is defined as a Completer Week 26 if the answer to the question "Did the subject complete the study?" is "Yes" on the End of Study CRF page and who received IP for at least 22 weeks.

7) Dates of First and Last Dose

The date of first dose of IP is defined as the date of first dose of IP documented on the First Dose of Study IP CRF page and the date of last dose of IP is defined as the date of last dose of IP documented on the End of Study 2 CRF page. If no date of first dose of IP is available, the date of randomization will be selected as the date of first dose of IP. If no date of last dose of IP is available, the date of completion/discontinuation documented on the End of Study CRF page will be selected as the date of last dose. If date of last dose of IP is not available and subject is lost to follow up based on End of Study CRF page, date of last scheduled visit or date of last telephone contact where an average daily dose is recorded, will be used as the date of last dose of IP.

8) Diabetes Disease Duration

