11.7 Efficacy Analyses

11.7.1 Key Secondary Endpoint

An overview of planned analyses for the key secondary endpoint of change from baseline in HbA1c, including sensitivity analyses, is provided in Table 5 below.

Table 5: Overview of key secondary endpoint analyses

Analysis	Population used	Analysis Details	Section reference
1. Main analysis	Full analysis set	Treatment Policy Estimand - ANCOVA using MI under the assumption of MNAR; this analysis uses unscheduled HbA1c results from discontinued subjects to impute missing in each treatment arm.	Section 11.7.1.1 Change from Baseline in HbA1c at 26 weeks

Gan & Lee Pharmaceuticals USA

PRA HEALTH SCIENCES

 Sponsor: Gan & Lee Pharmaceuticals, USA Corporation
 Protocol no: GL-GLAT2-3002

 Statistical Analysis Plan
 Version Date: 16-Nov-2020

Analysis	Population used	Analysis Details	Section reference
2. Sensitivity analysis	Per protocol analysis set	ANCOVA using MI under the assumption of MNAR; this analysis uses the same approach for imputation as the main analysis. Used to assess the robustness of main analysis to important deviations from the protocol.	Section 11.7.1.3 Sensitivity Analyses - PPS
3. Sensitivity analysis	Full analysis set of completers	ANCOVA without imputation. This analysis is used to assess the robustness of main analysis to subjects lost to follow-up.	Section 11.7.1.3 Sensitivity Analyses - FAS completers
4. Sensitivity analysis	Per protocol analysis set 3	ANCOVA using MI under the assumption of MNAR; this analysis uses the same approach for imputation as the main analysis. In the main analysis, subjects with efficacy-interfering deviations could falsely draw the estimated treatment difference closer. Exclusion of these subjects in this sensitivity analysis will help assess the magnitude, if any, of this effect.	Section 11.7.1.3 Sensitivity Analyses - Per Protocol Analysis Set 3
5. Sensitivity analysis	Full analysis set	Treatment Policy Estimand – MMRM will include all longitudinal HbA1c data points measured.	Section 11.7.1.3 Sensitivity Analyses - Mixed Model Repeated Measure
6. Sensitivity analysis	Full analysis set	ANCOVA using MI under the assumption of MNAR. This analysis uses unscheduled HbA1c results from discontinued subjects to impute missing in each treatment arm, with the addition of the term of presence/absence of ERIPD main effect and an interaction term of treatment*ERIPD.	Section 11.7.1.3 Sensitivity Analyses – ERIPD Interaction Analysis for Efficacy

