7. Sensitivity analysis	Full analysis set	ANCOVA using MI under the assumption of MNAR in each treatment arm for the following subgroups: Gender (male versus female), Age (< 65, versus ≥ 65 years old), Race (white versus non-white), BMI (Obese versus Non-obese), Menopausal Status (Pre- versus post-), Eligibility Criteria Met (Presence of an eligibility-related important protocol deviation versus no presence of an eligibility-related important protocol deviation).	Section 11.7.1.3 Sensitivity Analyses – Subgroup analyses
8. Tipping point analysis	Full analysis set	ANCOVA using MI under progressively severe departures from missing at random (MAR) assumption (i.e. MNAR assumption).	Section 11.7.1.3 Sensitivity Analyses - Tipping point analysis

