11.7.1.1 Change from Baseline in HbA1c at 26 weeks (Table 5, Analysis 1)

HbA1c values and change from baseline will be summarized by time point and treatment group.

HbA1c will be measured by a central laboratory in a single site in the US which is National Glycohemoglobin Standardization Program (NGSP) Level 1 certified. The estimand of interest on the HbA1c analysis is the difference in change from baseline for HbA1c using the "treatment policy strategy".

For subjects who discontinue from treatment before visit Week 26 or who have no HbA1c measurement at visit Week 26, HbA1c will be assigned to the scheduled time point if they fall within the allowed visit windows (visit Week 26 \pm 4 weeks).

Submissions to Food and Drug Administration (FDA) and European Medicines Agency (EMA) require different methods for efficacy HbA1c evaluation:

For FDA submission, equivalence in change from baseline in HbA1c between Gan & Lee Insulin Glargine Injection (μ_1) and Lantus[®] (μ_2) will be tested using the two one-sided tests (TOST) approach proposed in Schuirmann (1987) (7) with the following null hypothesis:

$$H_0: (\mu_1 - \mu_2) \leq -0.4 \text{ or } (\mu_1 - \mu_2) \geq 0.4$$

Against the alternative hypothesis of:

$$H_1: -0.4 < (\mu_1 - \mu_2) < 0.4$$

with $\alpha=0.05$.

The 90% CI will be estimated using a pattern mixture model that uses multiple imputation (MI) analyzed using Analysis of Covariance (ANCOVA) with treatment included as a fixed effect and baseline HbA1c included as a covariate. Separately in each treatment group, the imputation will use outcomes in subjects who discontinued treatment prior to Week 26 but returned to provide a visit Week 26 HbA1c sample to impute outcomes in subjects without actual visit Week 26 recorded results under the MNAR assumption. No imputation will be performed for missing baseline HbA1c. Equivalence will be assessed based on the 90% CI; no p-values will be computed. Change from baseline in HbA1c between Gan & Lee Insulin glargine Injection and Lantus[®] will be considered equivalent if the 90% CI is within the margins (-0.4%, 0.4%).

For EMA submission, non-inferiority in change from baseline in HbA1c between Gan & Lee Insulin Glargine Injection and Lantus[®] will be tested using the following null hypothesis:

$$H_0: (\mu_1 - \mu_2) \geq 0.4$$

Against the alternative hypothesis of:

$$H_1: (\mu_1 - \mu_2) < 0.4$$

with a 1-sided $\alpha=0.025$.

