In addition, the same non-inferiority test with a margin of 0.3% will be performed.

The 95% CI will be estimated using a pattern mixture model that uses multiple imputation analyzed using ANCOVA with treatment included as a fixed effect and baseline HbA1c included as a covariate. Separately in each treatment group, the imputation will use outcomes in subjects who discontinued treatment prior to Week 26 but returned to provide a visit Week 26 HbA1c sample (labeled as the unscheduled) to impute outcomes in subject without actual visit Week 26 recorded results under the MNAR assumption. No imputation will be performed for missing baseline HbA1c.

Analysis of HbA1c will follow a hierarchical testing strategy: first, non-inferiority will be tested using a margin of 0.4%, and only if this test is significant, then non-inferiority will be tested using a margin of 0.3%.

Sponsor: Gan & Lee Pharmaceuticals, USA Corporation
 Protocol no: GL-GLAT2-3002

Statistical Analysis Plan
 Version Date: 16-Nov-2020

Non-inferiority will be assessed based on the 95% CI; no p-values will be computed. Change from baseline in HbA1c between Gan & Lee Glargine Injection and Lantus® will be considered non-inferior if the 95% CI is below the margins of 0.4 and 0.3%, respectively.

For both, FDA and EMA submissions, to estimate the CI of the difference in HbA1c, the pattern-mixture model will be fitted using the SAS® procedure "MIXED" for FAS. A sample SAS code fragment is provided below for reference (note: actual seeds to be used in the analysis are presented below):

```
proc mi data=<data> nimpute=50 seed= 359648 out=<out_data>;
  by trt;
  class unscheduled;
  monotone reg(Week26_HbA1c=base_HbA1c);
  mnar model(Week26_HbA1c / modelobs = (unscheduled = '1'));
  var base_HbA1c;
run;
```

In between these steps, the data will be transposed and then the change from baseline at visit Week 26 will be calculated.

```
proc mixed data=<out_data> out=<lsmeans>;
  by _imputation_;
  class trt;
  model CFB_HbA1c_26 = trt base_HbA1c / ddfm=kr;
run;
proc mianalyze data=<lsmeans>;
  by effect;
  modeleffects estimate;
  stderr;
run;
```

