- 4) Mixed model repeated measure (MMRM): this sensitivity analysis will include all post-baseline HbA1c measures from each time point as the dependent variable. The independent variables in the model include fixed effects for treatment assignment (2 levels), time (3 post-baseline times), treatment-by-time interaction, and covariate terms for the baseline HbA1c score and baseline HbA1c score-by-time interaction (which allows the effect of baseline covariate parameter to change over time). An unstructured covariance matrix will be used to model the inter-dependencies among the repeated measures. However, if the model does not converge, an alternative covariance matrix will be used which is appropriate for the repeated measurements (e.g., first-order autoregressive). Given the missing data, the Kenward-Roger approximation will be used for calculating the denominator degrees of freedom and adjusting standard errors. If a structured variance-covariance matrix is used, sandwich estimator will be used to estimate the variance of the treatment effect estimate. The FAS will be used to generate the results. (Table 5, Analysis 5)

The SAS code to be used for the repeated measure model is:

```
Proc mixed data=<data>;
  class trt visit subject;
  model HbA1c = trt
        visit
        trt*visit
        base_HbA1c
        base_HbA1c*visit
        / solution ddfm=kr;
  repeated visit / subject = subj type=un;
  lsmeans treatment*visit / pdiff cl;
run;
```

- 5) ERIPD Interaction Analysis for Efficacy – To assess the impact of eligibility related treatment effect on efficacy, this analysis will be a repeat of the main analysis with the addition of the term of presence/absence of ERIPD main effect and an interaction term of treatment*ERIPD. The parameter estimate of the interaction term, 90% CI and p-value will be presented with least square means estimated for each ERIPD group under the treatment arms. (Table 5, Analysis 6)

Additional analysis examining the change from baseline in HbA1c at visit Week 26 in the following subgroups will be presented in a table and a forest plot, by treatment groups but not overall. Missing outcomes were imputed separately in each treatment group using outcomes in subjects who completed the study. These analyses will be conducted according to the FDA submission approach (i.e. 90% CI and 0.4% margin) with MI for the FAS (Table 5, Analysis 7):

- Gender (Male versus Female)
- Age (< 65 versus ≥ 65 years old)

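### The SAP text imputes missing Week 26 HbA1c in the subgroup analyses (Table 5, Analysis 7) from study completers, whereas the main analysis imputes from returned treatment discontinuers, and no reason is given

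*SAP*

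**What the plan says.** In SAP 11.7.1.3, the paragraph introducing the HbA1c subgroups (sex, age, race, BMI, menopausal status, eligibility criteria met) cites Table 5, Analysis 7 and states: "Missing outcomes were imputed separately in each treatment group using outcomes in subjects who completed the study". It applies the FDA approach, with a 90% CI and the 0.4% margin, in the FAS.

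The Table 5 row for the same analysis reads "ANCOVA using MI under the assumption of MNAR in each treatment arm for the following subgroups". It names no donors.

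For the main analysis, Table 5 says "this analysis uses unscheduled HbA1c results from discontinued subjects to impute missing in each treatment arm". SAP 11.7.1.1 agrees: "the imputation will use outcomes in subjects who discontinued treatment prior to Week 26 but returned to provide a visit Week 26 HbA1c sample". The sample code carries the same restriction, in the statement beginning "mnar model(Week26_HbA1c / modelobs = (unscheduled = '1".

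Protocol 12.8.1 had a different method under missing at random: "the imputation will use the outcomes of patients who completed the study". There, completers expressly include treatment discontinuers who gave a Week 26 sample. SAP 3.1 declares the move to returned discontinuers and MNAR, following an FDA suggestion and provided there are enough data.

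**The concern.** The subgroup sentence follows the protocol's method, which SAP 3.1 replaced for the main analysis. Its past tense, unusual in a plan, also suggests carried-over text, though that is an inference. Followed as written, the same subjects would have one set of imputed Week 26 values in the main analysis and another in the subgroup table and forest plot.

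The clearest clash is over ERIPD. Analysis 6 examines it by interaction, with least-squares means by ERIPD group, under the main imputation. Analysis 7 examines it as a subgroup under the completer sentence. The report could then show two sets of results on one question that differ partly because of the imputation.

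Missing data are not a remote issue: SAP 5.1 reports more early discontinuation than expected. If the choice is left open, it falls to whoever programs the analysis, possibly after the blinded team is unblinded at database lock.

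**Working it through.** The plan states no figure on this point, so there is none to reproduce. The check is a comparison of the texts, then an illustration of size.

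**Texts side by side**

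| Place | Donors, by arm | Label |
|---|---|---|
| Protocol 12.8.1 | Study completers, including treatment discontinuers with a Week 26 sample | MAR |
| SAP 3.1 | Treatment discontinuers with Week 26 HbA1c, if data suffice | MNAR |
| SAP Table 5 row 1, 11.7.1.1 and code | Treatment discontinuers who returned | MNAR |
| Table 5 rows 2 and 4 (PPS, PPS3) | As main analysis | MNAR |
| 11.7.1.3, PPS fallback | Everyone with a Week 26 result | MNAR |
| Table 5 row 6 (ERIPD interaction) | As main analysis | MNAR |
| Table 5 row 7 (subgroups) | Not named | MNAR |
| 11.7.1.3, subgroup text | Study completers | None given |

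The last row is the only one in the SAP that names completers as donors. The firm conflict is between it and the main analysis.

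**Shift in the treatment difference.** Let f be the missing share in an arm and d the mean of returned discontinuers minus the mean of completers, ignoring baseline adjustment. Moving from completer donors to returned donors changes the arm mean by f × d, so the treatment difference changes by f_T × d_T − f_C × d_C. The assumed ranges are f from 5% to 20% and d from 0 to 1.0 point.

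| f_T, f_C | d_T, d_C | Shift |
|---|---|---|
| 10%, 10% | 0.5, 0.5 | 0.05 − 0.05 = 0 |
| 10%, 15% | 1.0, 1.0 | 0.10 − 0.15 = −0.05 |
| 15%, 15% | 0.5, 0 | 0.075 − 0 = 0.075 |
| 15%, 10% | 1.0, 0.5 | 0.15 − 0.05 = 0.10 |
| 20%, 10% | 1.0, 0.5 | 0.20 − 0.05 = 0.15 |

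The last line is 0.15/0.4 = 37.5% of the margin. The extreme corner of the ranges, 20% missing with a gap of 1.0 in one arm and no gap in the other, gives 0.20 × 1.0 − 0 = 0.20.

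**If completers include returned discontinuers.** Let w be the share of returned subjects among the donors. Each arm's term is then multiplied by (1 − w). With 275 per arm and 10% missing, 247.5 are observed. With 10 returned, w = 10/247.5 = 4%, and with 20 returned, w = 20/247.5 = 8%. The reduction is small when few return.

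**Width of the 90% CI.** Assume residual SD 1.0 and n = 275 per arm, with n_m missing, n_r returned and n_o on schedule. The variance of an arm mean is:

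- completer donors: SD² × [(n_o + n_m)²/n_o + n_r]/n²
- returned donors: SD² × [n_o + (n_r + n_m)²/n_r]/n²

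The half-width is 1.645 × √(2 × variance). For 10% missing and 10 returned, n_m = 27.5 and n_o = 237.5:

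- completer donors: (265²/237.5 + 10)/275² = 0.00404, half-width 0.148
- returned donors: (237.5 + 37.5²/10)/275² = 0.00500, half-width 0.165

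With 5 returned and 10% missing, the returned-donor half-width is 0.180 against 0.148. With 5 returned and 15% missing, it is 0.217 against 0.152. These are whole-arm widths and show direction only.

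**The case against.** Several stronger readings are tempting, and the documents do not support them.

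- A reader might infer that Table 5 row 7 contradicts the text on donors. The row names none, and the SAP attaches the MNAR label even to the PPS fallback, which imputes from everyone with a Week 26 result. The label does not fix the donor set.
- A reader might infer that the completer sentence treats dropouts as if they had stayed on treatment. That holds if the SAP's Completer Week 26 definition applies, since it requires a subject "who received IP for at least 22 weeks". Under the protocol's meaning, some donors were off treatment. The sentence cites neither definition.
- A reader might infer that the main analysis was changed to avoid this. SAP 3.1 records only an FDA suggestion.
- A reader might expect subgroup estimates to average to the overall estimate. Separate ANCOVAs, each with its own baseline slope, need not do so even under identical imputation. Menopausal status does not partition the FAS, and the planned plot has no overall row.

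A wider donor set might also be defended because few discontinuers return. SAP 3.1 does make the main method conditional on enough data. But the subgroup sentence imputes by arm, not within subgroup, so its pool of returned subjects would be the same as in the main analysis. The SAP writes out a sparse-donor fallback only for the PPS.

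What stands of the objection is that the numerical effect may be nil and that nothing confirmatory depends on it. The conflict over donors remains.

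**Conclusion.** The inconsistency is real and minor. The SAP specifies a completer donor set for Analysis 7 that differs from the main analysis and from the neighbouring PPS, PPS3 and ERIPD interaction analyses, without giving a reason.

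The size cannot be fixed from the documents. Under the assumed ranges, the change in the treatment difference is 0 when missing share and gap are alike in both arms. It is about 0.15 points in the largest tabulated combination and 0.20 in the most lopsided corner, and somewhat less if completers include returned discontinuers. Within a subgroup, the relevant f is that subgroup's own missing share. Completer-based intervals would be narrower in the cases worked, and too narrow if the main-analysis assumption is the intended one.

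A reader might infer that the HbA1c conclusion is at risk. It is not: the subgroups are supportive and lie outside the testing hierarchy, so the equivalence and non-inferiority conclusions are unaffected.

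**What to change.** Before database lock, replace the completer sentence in SAP 11.7.1.3 and complete Table 5 row 7 so that both name the main-analysis donors: by arm, subjects who discontinued treatment and returned at Week 26. State that the ANCOVA will be fitted within each subgroup level to each of the 50 data sets imputed for the main analysis and the results combined. Analyses 6 and 7 would then use the same imputed values.

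Two notes should accompany the change. First, the main imputation model contains only baseline HbA1c within arm, with no subgroup term, so imputed values may pull subgroup results together. This is a small limitation that the current by-arm sentence shares. Second, if returned donors are too few, Analysis 7 should take whatever fallback governs the main analysis. Reusing the data sets achieves this, but the SAP should write that fallback out, since it now does so only for the PPS.

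The cost is one sentence and one table cell, with less programming than a second imputation.
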